6.1.5. Manufacturing, Packaging and Labelling

Manufacturing including packaging and labelling will be carried out in accordance with the GMP guidelines (including their Annexes), ICH GCP requirements, sponsor approved standard operating procedures, The European Union (EU) Clinical Trial Directive and all applicable local laws.

Final labelling and packaging of the products will be performed by the Production Operations Department of Biologische Heilmittel Heel GmbH in accordance with their standard operating procedures (SOPs) and international requirements. Product labels comply with the relevant GCP requirements including national regulatory requirements and languages.

6.1.6. Shipment and Storage of IMP

IMP will be supplied to the sites together with the relevant documentation. The site staff will acknowledge the receipt of all shipments via fax or email.

IMP will be handled by the team member responsible exclusively for handling the study medication. He/she will be appointed by the principal investigator.

IMP has to be stored in an appropriate secure area (e.g. a locked cabinet) not above 25°C and not frozen, as indicated in the packaging.

The IMP is to be dispensed only under the restricted conditions defined in the present protocol (see 6.1.5).

All returned IMP will be stored in zipped bags until destruction.

6.1.7. IMP Accountability and Destruction

Each center will be responsible for maintaining an accurate log and inventory of IMP received, dispensed and returned. The designated CRO will provide the framework for documenting study drug accountability throughout the study. The team member responsible exclusively for handling the study medication has to record the shipment, dispense, and return of IMP on the *drug accountability form*. The *drug accountability form* needs to be available for inspection at any time. Data of the investigational product dispense, use and return will be entered into the eCRF.

The designated CRO representatives will verify drug accountability during routine site monitoring visits and at the completion of the trial. An explanation of any discrepancies has to be provided by the responsible team member.

Detailed drug accountability has to be performed for remaining unused and returned used IMP. Remaining and returned IMP tubes and copies of the completed *drug accountability forms* will be sent back to Heel for destruction by the team member responsible exclusively for handling the study medication after last patient last visit. Certificates of returns have to be signed by the responsible person(s).

6.1.8. Treatment Compliance

The compliance with investigational treatment will be ensured by weighing the gel tubes returned by the patient at Day 4 and finally at Day 7. Afterwards the team member responsible exclusively for handling the study medication will seal the used tubes in zipped bags.

6.1.9. Rescue Medication

Randomised patients will receive Paracetamol (acetaminophen) 500 mg/tablets as a rescue medication to be taken for pain relief when necessary (*pro re nata*, PRN), with a maximum dose of four tablets or 2000 milligrams per day (mg/d), and not more than 2 tablets at a time. Patients will not be allowed to take paracetamol within 8 hours prior to visit 2. For further visits the restriction is 24 hours, consequently taking paracetamol will not be allowed within 24 hours prior to visit 3, visit 4 and visit 5. Other allowed and prohibited concomitant medications are described in section 6.2.

Randomised patients will also receive a patient diary and will be instructed to document the time and dose of each intake of the rescue medication (paracetamol) in a patient diary every day and to bring the patient diary to the site at each patient visit. Site staff will check the patient diary at all visits if rescue medication has been taken at all, and if yes, according to the requirements.

In addition, it is essential that time and dose of all paracetamol tablet intakes (rescue medication) are documented by the site staff in the eCRF.

The site will record the total number of tablets taken by the patient from one visit to the next on the *rescue medication accountability form*. Patient Diary 1 will be used between visits at Day 1 and Day 4, it will be collected by the site staff on Day 4 and will be replaced with Patient Diary 2, which will be used until end of the study.

6.1.10. Supportive Therapy

All patients will receive soft support (elastic bandage) on Day 1. The team member responsible exclusively for handling the study medication will train all patients how to use the elastic bandage and - if needed - for the usage of the semi-rigid brace.

Re-evaluation of grading will be performed at Day 4. Grade 1 patients will continue using the soft support during the entire trial, as required (*revised per Amendment to protocol version 3.0*). Grade 2 patients will receive a semi-rigid removable brace on Day 7. Grade 3 patients will be withdrawn from the trial and further treatment will be at the discretion of the investigator. The semi-rigid braces will be provided to all patients centrally and the investigator team will be trained for correct use at the investigator meeting and/or at Site Initiation Visits and/or during regular Monitoring Visits to ensure standardized circumstances. In addition, it will be strongly recommended to all patients to use arm crutches during the entire trial and with a special importance until Day 4. The patients should only partly weight the sprained ankle when using crutches.

Use of arm crutches and semi-rigid braces will be recorded on the medical records and entered into the eCRF.

The use of RICE (simultaneous combination of all 4 elements rest, ice, compression, and elevation) is restricted to the time immediately after the event, and before starting treatment with the investigational drug. After start of study treatment and during the entire course of the trial use of RICE is prohibited. If it occurs, it will be recorded on medical records and entered into the eCRF.

6.2. Prior and Concomitant Medications

Use of local or systemic corticosteroids is not allowed 8 weeks before screening and during the study. Long-acting NSAIDs, COX-2 specific inhibitors, tramadol or other opioids are not allowed within 48 hours, and any other analgesics (e.g. acetaminophen) are not allowed within 24 hours prior to the screening /baseline visit and during the study. Disallowed medication includes all forms of those medications, i.e. topical, oral or parenteral.

Low dose (70-100 mg/day) acetylsalicylic acid for anti-thrombotic therapy is permitted if doses are stable for the month prior to screening and expected to remain stable throughout the study period.

Patients have to be instructed that they must not take any pain relief medication other than the provided paracetamol rescue medication during the entire study period, see section 6.1.9 for details. Any intake of pain medications other than the rescue medication will be recorded in the patient diary and entered into the eCRF.

Antithrombotic treatment may be given at the discretion of the investigator in accordance with currently valid guidelines.

Medications required for treatment of symptoms/diseases that are totally unrelated to the treated indication and related disorders are permitted during the trial and have to be documented in the eCRF (including name of the medication, date of administration and its duration, and indication for use).

7. Study Procedures

7.1. Schedule of Study Procedures

A schedule of study procedures and events is provided in Table 1.

Table 1 Schedule of Study Procedures

| | Initial Visit | Treatment Visits | | EoT Visit | Final Visit |
|--|--------------------|------------------|------------------|--------------------|---------------------|
| | Screening/Baseline | Visit 2 | Visit 3 | Visit 4 | Visit 5 |
| | Day 1 | Day 2 | Day 4 + 1 day | Day 7 +/- 1 day | Day 14 +/- 1 day |
| Informed Consent | X | | | | |
| Inclusion/Exclusion Criteria | X | | | | |
| Demographics | X | | | | |
| Pregnancy test (if applicable) | X | | | X | |
| Medical history | X | | | | |
| Time and grading of injury | X | | | | |
| Height/Weight (BMI) ¹ | X | | | | X ¹ |
| Physical examination including blood pressure and pulse | X | | | | X |
| Randomization | X | | | | |
| Dispense patient diary ² | X | | X | | |
| FAAM-ADL ³ | X | X | X | X | X |
| Pain at rest by Visual Analog Scale (VAS) ³ | X | X | X | X | X |
| Pain on passive movement by Visual Analog Scale (VAS) ³ | X | X | X | X | X |
| IMP tubes dispensed | X | | | | |
| Investigational treatment | X | X | X | X | |
| Application of soft support (elastic bandage) | X | X | X | X (as required) | X (as required) |
| Rescue medication dispensed | X | | X (if needed) | X (if needed) | |
| Diary reviewed | | X | X | X | X |
| Diary returned | | | X | | X |
| IMP tubes weighted | | | X | X | |
| Rescue medication reviewed | | X | X | X | X |
| IMP tubes returned and sealed | | | | X | |
| Rescue medication returned | | | | | X |
| Check use of other pain medication and record if any | X | X | X | X | X |
| Record previous/concomitant medication | X | X | X | X | X |
| Record Adverse Events ⁴ | X | X | X | X | X |
| Record use of arm crutches | X | X | X | X | X |
| Confirmatory check of grading | | | X | | |
| Application of semi-rigid brace for Grade 2 | | | | X | X |
| Question to patients which treatment they assume to have received | | | | | X |

¹ At Visit 5 (day 14) only the weight will be measured.

² The first patient diary will be collected on Day 4. The patient will receive second diary on the same day. ³

The time point of each visits/ measurements of patients shall be ideally the same at each visit (+/- 1 hour). ⁴

Including adverse events observed at the site of administration of the IMP (lateral ankle).

7.2. Description of Patient Visits

7.2.1. Screening / Baseline Visit (Day 1)

Day 0 is defined as the day of injury. The day of inclusion to the study is Day 1. If the patient is included into the study on the same day when the injury has occurred, Day 0 and Day 1 are identical. The date and time of injury and date and time of the first treatment with investigational drug has to be documented in the eCRF to ensure that the time difference between both events does not exceed 24 hours.

Suitable outpatients will be asked by the investigator about their willingness to be included in the clinical trial. The patient is to be informed verbally and in writing in the appropriate language about the nature and purpose of the study, the treatments to be administered, the possible risks and discomfort, the benefits to be expected, and how data collected in this trial will be handled and shared. The patient informed consent form is to be signed and dated by the patient and countersigned by the investigator prior to proceeding with the Screening/ Baseline Visit procedures. The investigator will provide each patient with a second original of the signed and dated informed consent form. See section 1.3 for more details.

Patients who have signed the patient informed consent form will be assessed if they meet all inclusion but none of the exclusion criteria.

Only patients who fulfil all entry criteria will be enrolled and will receive a unique 7-digit patient number (in former protocol versions referred to as 'E-code').

The following study procedures are to be performed:

- Check of inclusion/ exclusion criteria
- Record medical history and demographics
- Review and record previous/ concomitant treatments for the sprained ankle including use of RICE (i.e., the simultaneous combination of all 4 elements rest, ice, compression and elevation) or of parts of these 4 measures
- Review and record previous/concomitant treatments for any other clinical condition(s) also with respect to disallowed medication
- Ankle sprain-related measurements:
 - FAAM-ADL

-
- VAS for evaluating pain at rest for baseline. VAS for pain on passive movement by investigator for inclusion and for baseline. Date and time of assessment will be recorded. Each pain assessments should take place at the same time (+/- 1 hour related to baseline assessment time) at each visit whenever possible
 - Physical examination of cardiovascular, respiratory, musculoskeletal and gastrointestinal systems, head and eyes
 - Measurement of body weight and height, (for body mass index), blood pressure and heart rate
 - Pregnancy test (urine dipstick) for women of childbearing potential.

7.2.2. Randomization

- Patients who fulfil all the inclusion criteria and do not meet any of the exclusion criteria will be randomised to the investigational treatment and will receive Traumed[®] gel or diclofenac gel or placebo gel. (See section 6.1.2)
- The team member responsible exclusively for handling the study medication will dispense IMP to the patient, will apply the first dose and will train the patient how to use the dosage card and the IMP.
- The team member exclusively responsible for handling the study medication will train the patient how to use the elastic bandage and place the elastic bandage (soft support)
- Paracetamol (500 mg/tablet) will be dispensed as rescue medication for pain relief with a maximum dose of four tablets or 2000 mg/day, but not more than 2 tablets at a time. Patients are to be instructed to refrain from taking any analgesic medication other than the provided rescue medication and that they are not allowed to take paracetamol neither within 8 hours prior to visit 2. (For further visits the restriction will be 24 hours, consequently taking paracetamol will not be allowed within 24 hours prior to visit 3, visit 4 and visit 5).
- Patient diary will be distributed to the patient. The patient will be instructed to document the date, time and amount of paracetamol intake every day and to bring the diary to the site at each visit. In addition, the patient will be requested to document other concomitant medications in the diary and to record how many times he/she has applied the IMP on each day. The site staff will transfer the paracetamol consumption since last patient visit (including date, time, and amount of consumed tablets) and the IMP use from the diary into the eCRF.
- The patient will be strongly suggested to use arm crutches during the entire trial and with a special importance until Day 4

- Evaluation of any AEs experienced after informed consent has been signed, including AEs observed at the site of administration of the IMP (lateral ankle). SAE evaluation and reporting if applicable
- Patients will be instructed to return to the next visit (+/- 1 hour related to baseline assessment time) and return patient diary, IMP and remaining rescue medication

7.2.3. Treatment Visit 2 (Day 2)

The following observations/ procedures are to be performed and checked:

- FAAM-ADL (+/- 1 hour related to baseline assessment time whenever possible)
- Removal of the elastic bandage by the team member responsible exclusively for handling the study medication
- Ankle sprain-related measurements: VAS for evaluating pain at rest and pain on passive movement (+/- 1 hour related to baseline assessment time whenever possible)
- Review of rescue medication usage recorded in the patient diary and transfer data into the eCRF
- Check other (prohibited) pain medication and/or whether RICE was used with the patient (RICE is prohibited, i.e. the simultaneous combination of all 4 elements rest, ice, compression and elevation; parts of these 4 measures are acceptable), record on medical records and enter into the eCRF if any
- Record any change in other concomitant medications
- Record use of arm crutches
- Evaluation and recording of any AEs the patient has experienced since the last visit including possible re-injury of the ankle and adverse events observed at the site of administration of the IMP. SAE evaluation and reporting if applicable
- Application of IMP and elastic bandage by the team member exclusively responsible for handling the study medication
- Drug accountability for rescue medication
- Instruct the patient that he/she is further not allowed to take any analgesic medication other than the rescue medication provided by the study site staff (paracetamol) with a maximum dose of four tablets or 2000 mg/day, but not more than 2 tablets at a time. He/she will not be allowed to take any tablets of it within 24 hours prior to visit 3.
- Instruct the patients to return to next visit (+/- 1 hour related to baseline assessment time) and return patient diary, IMP and remaining rescue medication.

7.2.4. Treatment Visit 3 (Day 4 +/- 0 day)

The following observations/ procedures are to be performed and checked:

- FAAM-ADL (+/- 1 hour related to baseline assessment time whenever possible)
- Removal of the elastic bandage by the team member exclusively responsible for handling the study medication
- Ankle sprain-related measurements: VAS for evaluating pain at rest and pain on passive movement (+/- 1 hour related to baseline assessment time whenever possible)
- Review of rescue medication and IMP usage recorded in the patient diary and transfer data into the eCRF
- Check other pain medication and/or RICE use with the patient (both are prohibited), record on medical records and enter into the eCRF if any
- Record any change in other concomitant medications
- Record use of arm crutches
- Evaluation and recording of any AEs the patient has experienced since the last visit including a possible re-injury of the ankle and adverse events observed at the site of administration of the IMP. SAE evaluation and reporting if applicable
- Collection of patient diary used from Day 1 to Day 4 and dispense patient diary to be used from Day 4 to Day 14
- Confirmatory check of grading. Patients with severity Grade 3 will be withdrawn from the study. No further data will be collected from these patients. Further treatment and taken care will be at discretion of the investigator according to the local medical practice.
- Drug accountability for IMP by weighing of study drug tube by the team member exclusively responsible for handling the study medication
- Application of IMP (and elastic bandage, if still required) by the team member exclusively responsible for handling the study medication
- Drug accountability for rescue medication
- Dispense 500 mg paracetamol tablets (one box containing 20 tablets) as rescue medication for pain relief (if needed). Instruct the patient that he/she is further not allowed to take any analgesic medication other than the rescue medication (paracetamol) provided by the study site staff with a maximum dose of four tablets or 2000 mg/day, but not more than 2 tablets at a time. He/she will not be allowed to take any paracetamol tablets within 24 hours prior to visit 4.

-
- Instruct patients to return to next visit (+/- 1 hour related to baseline assessment time) and return patient diary, IMP and remaining rescue medication.

7.2.5. End of Treatment Visit (Visit 4; Day 7 +/- 1 day) or Discontinuation of Treatment Visit if applicable

The following observations/procedures are to be performed and checked:

- FAAM-ADL (+/- 1 hour related to baseline assessment time whenever possible)
- Removal of the elastic bandage by the team member exclusively responsible for handling the study medication
- Ankle sprain-related measurements: VAS for evaluating pain at rest and pain on passive movement (+/- 1 hour related to baseline assessment time whenever possible)
- Pregnancy test (urine dipstick) for women of childbearing potential
- Review of rescue medication and IMP usage recorded in the patient diary and transfer data into the eCRF
- Check other pain medication and/or RICE use with the patient (both are prohibited), record on medical records and enter into the eCRF if any
- Record any change in other concomitant medications
- Record use of arm crutches
- Evaluation and recording of any AEs the patient has experienced since the last visit including possible re-injury of the ankle and adverse events observed at the site of administration of the IMP. SAE evaluation and reporting if applicable
- Last application of IMP by the team member exclusively responsible for handling the study medication.
- Application of elastic bandage for patients with Grade 1 ankle sprain (if still required), and semi-rigid brace for patients with Grade 2 ankle sprain by the team member exclusively responsible for handling the study medication (grading based on confirmation check of grading performed at Day 4)
- Drug accountability for IMP, weighting and collection of study drug tube by the team member exclusively responsible for handling the study medication
- Drug accountability for rescue medication
- Dispense 500 mg paracetamol tablets (one box containing 20 tablets) as rescue medication for pain relief (if needed). Instruct the patient that he/she is further not allowed to take any analgesic medication other than the rescue medication (paracetamol) provided by the study site staff with a maximum dose of four tablets or

2000 mg/day, but not more than 2 tablets at a time. He/she will not be allowed to take any paracetamol tablets within 24 hours prior to visit 5

- Patients will be instructed to return to the next visit (+/- 1 hour related to baseline assessment time) and return patient diary and remaining rescue medication.

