5.1. Overall Design and Plan of the Study

This is a multicentre, double-blind, randomised, active- and placebo-controlled, parallel-group study.

After evaluation of entry criteria patients with grade 1 or 2 unilateral ankle sprain will be randomised to study treatment. The treatment will be 3 g of Traumed[®] gel or diclofenac gel or matching placebo gel, administered locally to sufficiently cover the area of the injury, 3 times daily for 7 days. The first treatment will be administered following the baseline study procedures and after randomisation of the patient on Day 1.

After end of investigational treatment patients will be followed up for another 7 days. Consequently, the entire duration of the study for each patient will be 14 days.

Patients will receive paracetamol (acetaminophen) 500 mg/tablet as rescue medication to be taken for pain relief when necessary (*pro re nata*, PRN) during the entire duration of the trial, see section 6.1.9 for further details. In addition, patients will not be allowed to take any pain relief medication other than the provided paracetamol, see section 6.2 for details.

All patients will receive soft support (elastic bandage) on Day 1. There will be a re-evaluation of grading of the disease at Day 4. Patients whose classification will be changed to Grade 3 will be withdrawn from the study. Grade 1 and grade 2 patients will continue using the soft support during the entire study, if required. Grade 2 patients will additionally receive a semi-rigid removable brace on Day 7, see section 6.1.10 for detailed description. It will be strongly recommended to all patients to use arm crutches during the entire trial and with a special importance until Day 4. The patients should only partly weight the sprained ankle when using crutches.

The study will start with the recruitment of the first patient. End of trial is defined as completion of the data base lock.

The study was originally planned to be started in Q1/2018. The first patient was screened on February 26th, 2018. The extended duration of the recruitment period will be approximately 35 months and will be completed when at least 808 eligible patients have been enrolled. (*revised per Amendment to protocol version 3.0*)

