5.3. Selection of Study Population

Patients with acute unilateral Grade 1 or Grade 2 sprain of the lateral ankle will be enrolled. Grade 3 patients are not eligible as for them topical gel treatment is not appropriate.

Ankle sprains are classified by 3 grades of sprains:

- Grade 1 sprain (mild): Slight stretching and some damage to the fibres (fibrils) of the ligament. The joint is stable.
- Grade 2 sprain (moderate): Partial tearing of the ligament. If the ankle joint is examined and moved in certain ways, abnormal looseness (laxity) of the ankle joint occurs. Clinically partial instability.
- Grade 3 sprain (severe): Complete tear of the ligament. If the investigator pulls or pushes on the ankle joint in certain movements, gross instability occurs. The joint is instable.

Fracture of the ankle should be excluded by using e.g. the Ottawa Ankle Rules. In case of any doubt the exclusion of fracture by x-ray should be considered as per standard of care. After excluding fracture the investigator will evaluate the stability of the ankle joint using the anterior drawer test, the inversion stress manoeuvre and the external rotation test.

The mechanism of the injury and the clinical symptoms (edema, hematoma, location of pain at palpation) will be documented to support the grading.

The high pain and swelling might influence the outcome of the grading at Day 1, therefore a confirmatory check of the grading will be performed at Day 4. Patients who are classified having Grade 3 ankle sprain after randomisation and up to Day 4 will be withdrawn from the study and their data will not be part of the efficacy analysis but will be part of the safety analysis.

The investigators will be trained during the investigator meeting to ensure a consistent assessment and grading between investigators.

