5.3.3. Discontinuation of Treatment

Patients who meet any of the discontinuation criteria will discontinue investigational treatment and will be followed up only for AEs until Day 14.

Study investigators may request the patient to discontinue investigational treatment in case of:

- Diagnosis of Grade 3 ankle sprain
- Any other medical condition requiring in the opinion of the investigator a change of the therapy for the baseline condition
- Occurrence of a medical condition requiring use of prohibited medications or treatment
- Medical condition affecting assessment of the primary endpoint
- Medical conditions affecting patient safety if the investigational therapy is continued: conditions and AEs causing safety concerns with investigational treatment to the ankle

joint area OR any other AE or condition that - in the opinion of the investigator – endangers patient safety if the investigational therapy is continued

- Lack of efficacy as considered by the investigator.

Discontinuation of investigational treatment and its reason will be documented in the medical records and recorded in the eCRF. If a patient discontinues investigational treatment, the discontinuation of treatment visit should be performed. Further treatment of the ankle sprain will be at discretion of the investigator and will not be recorded in the eCRF. In case the patient will be treated in another hospital or practice, the investigator will make efforts to collect and record AEs the patient might have had until Day 14. This can be done during an onsite visit or a phone call with the patient or with the treating physician at the other hospital or practice. Patients who discontinue prematurely from the study will not be replaced, except patients with Grade 3 sprain confirmed at any day up to Day 4 ('replacement' referring to the total number of patients to be enrolled, see also definitions in section 11.4).

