5.3.4. Withdrawal of Patients from the Study

Reasons for premature withdrawal (drop out) from the study:

- Diagnosis of Grade 3 ankle sprain at any day up to Day 4
- The patient does not fulfil all inclusion criteria and/or meets any of the exclusion criteria but was randomised by error
- Pregnancy
- Lost to follow up
- Death
- Withdrawal of consent.

Withdrawal from study including its reason will be documented in the medical records and entered into the eCRF. In case the reason for withdrawal from study is withdrawal of consent, the patient will be asked why he/she withdrew his/her consent. The specified reason will be also recorded in the medical records and entered into the eCRF. No further investigational treatment will be used and/or assessments will be performed for withdrawn patients. In case of an ongoing AE, the patient is to be followed up according to the local medical practice.

5.3.5. Study Site Discontinuation by the Sponsor.

The Sponsor may prematurely close a study site at any time for any of the following reasons:

-
- occurrence of AEs or other safety issues requiring early withdrawal of at least 25% of enrolled patients (if 20 or more of planned patients are enrolled)
 - failure to enroll patients, i.e. no patients enrolled after 3 months from site initiation
 - persisting occurrence of significant protocol violations affecting patient safety in already enrolled patients
 - inaccurate or incomplete data affecting evaluability of patients in final analysis
 - significant administrative problems including GCP violations or misconduct of the study which may jeopardize the quality of study.

The reasons for the discontinuation of the study at a study site have to be communicated in writing to the IEC of the relevant site. Afterwards the close-out site visit has to be performed.

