9.1.3. Medical Events not to be Considered Adverse Events or SAEs

The following events should not be recorded as an AE/ SAE if recorded at the Screening/ Baseline Visit and/or the basic examination of a clinical trial:

- A pre-planned procedure, e.g. surgery and invasive procedures, unless the condition for which the procedure was planned has worsened since baseline. Complications to pre-planned procedures should be recorded as AEs.
- A pre-existing condition found as a result of Screening/ Baseline Visit procedures.
- Variations in chronic disease symptoms and in related investigational results if similar variations were observed earlier. These include symptoms and their intensity that are requested and documented in the eCRF, Diary or Questionnaire at the respective visits.
- Compromised or biologically implausible test results, e.g. mechanical or physical effects on blood samples or values incompatible with life, respectively.
- Pregnancy is not considered to be an AE.

Note: Any worsening in severity or frequency of a concomitant illness or any new illness diagnosed in the study period has to be regarded as AEs/SAEs.

In this clinical trial deterioration of ankle sprain symptoms will not be recorded as an AE/SAE.

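### Dosed patients withdrawn for Grade 3 sprain up to Day 4 stay in the Safety Analysis Set, but active AE collection stops at withdrawal instead of running to Day 14

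*Protocol*

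**What the plan says.** - **Withdrawal.** Protocol 5.1: "Patients whose classification will be changed to Grade 3 will be withdrawn from the study". Sections 5.3, 5.3.4, 6.1.10 and 7.2.4 give the same instruction; 5.3 and 5.3.4 limit it to Grade 3 found up to Day 4.
- **Analysis set.** Protocol 5.3, on the same patients: "their data will not be part of the efficacy analysis but will be part of the safety analysis". Section 11.1.1 puts every randomised patient with at least one dose in the Safety Analysis Set, and SAP 9.7.1.1 repeats this.
- **Data after withdrawal.** Protocol 5.3.4: "No further investigational treatment will be used and/or assessments will be performed for withdrawn patients". Protocol 7.2.4: "No further data will be collected from these patients".
- **Early treatment stoppers.** Protocol 5.3.3 says that patients who meet a discontinuation criterion "will be followed up only for AEs until Day 14". If such a patient is treated elsewhere, the contact can be simple: "This can be done during an onsite visit or a phone call with the patient". A Grade 3 diagnosis is on the 5.3.3 list with no day limit.
- **Partial cover after withdrawal.** Protocol 5.3.4: "In case of an ongoing AE, the patient is to be followed up according to the local medical practice". Section 9.4 keeps AEs reportable after a patient's study has ended if the investigator links them to the product. Section 9.1.3 removes one class of event: "In this clinical trial deterioration of ankle sprain symptoms will not be recorded as an AE/SAE".

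The SAP safety sections (9.6 and 9.7) add no rule for these patients.

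**The concern.** Two kinds of patient who leave treatment early share one AE denominator but are observed differently. A patient stopped on Day 3 for lack of efficacy is followed for AEs to Day 14. A patient withdrawn on Day 3 for Grade 3 sprain is not, although the trial ended that participation and the patient did not withdraw consent. The protocol gives no reason for the difference.

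Tolerability and safety of Traumed gel is a stated secondary objective. Section 11.1.5 plans incidence rates for all AEs and SAEs, not only related ones. A patient observed for about 4 days counts in those rates as if observed for 14, so the rates are pulled down.

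**Working it through.** **1. Which rule applies.** Section 5.3.4 is specific and limited to Day 4. Section 5.3.3 is general and has no day limit. The natural reading is that 5.3.4 governs up to Day 4 and 5.3.3 governs later cases. The protocol does not say so, but the gap exists on that reading, so the rest of the check uses it.

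**2. Days without active collection.** Follow-up is 14 days (5.1). For a patient withdrawn at the Day 4 re-grading, 14 − 4 = 10 days are uncovered. Re-grading is scheduled only at Visit 3, so this is the main case; a Grade 3 found earlier would lose more.

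**3. Bias in all-AE incidence.**
- AE rate p = 14/148 = 9.46% (Traumeel gel group of the earlier ankle sprain trial, Protocol section 3).
- Share of the Safety Analysis Set withdrawn for Grade 3, r: not in the documents; 1%, 5% and 10% are assumed.
- If AEs are spread evenly over 14 days (assumption): bias = p × r × 10/14.
- If all AEs fall in the first 7 days (alternative assumption): bias = p × r × 3/7.

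| r | Even spread | Reported rate | First 7 days only | Reported rate |
|---|---|---|---|---|
| 1% | 0.07 points | 9.39% | 0.04 points | 9.42% |
| 5% | 0.34 points | 9.12% | 0.20 points | 9.26% |
| 10% | 0.68 points | 8.78% | 0.41 points | 9.05% |

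Three things make these figures high. The earlier trial reported results out to 6 weeks, so 9.46% may cover a longer period. The gel stops at withdrawal. Related AEs stay reportable.

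**4. Number of patients.** Section 5.3.3 replaces Grade 3 cases found up to Day 4, so they come on top of the planned 404 Traumed patients: 404 × r/(1 − r) = 4.1, 21.3 or 44.9 extra. Patients with a missed AE under even spread = (404 + extra) × p × r × 10/14 = 0.28, 1.44 or 3.03. Planned observation is 404 × 14 = 5656 patient-days. With the extra patients at 4 days each it is 5672, 5741 or 5836, so none is lost.

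**5. The 1% AE detection aim (11.4).** The plan's figures reproduce: ln(0.05)/ln(0.99) = 298.07, rounded up to 299, with 1 − 0.99^299 = 95.05%; and 299/0.96 = 311.5, rounded up to 312.
- With 404 fully followed patients, detection is 98.3%.
- Ignoring replacement, and counting 3 of the 13 days from Day 1 to Day 14 as observed in affected patients, it is 98.2%, 98.0% or 97.6% at r = 1%, 5% or 10%.
- The SAP reports 184 issue patients separately. If they split 2:1:1 (assumption), 92 are Traumed, leaving 404 − 92 = 312 and a detection probability of 95.65%. Without replacement, r = 10% would bring this to 94.5%; with the replacement rule it stays at 95.65% or above.

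**The case against.** The strongest case against the point has four parts.

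- **There is no real conflict between sections.** Five sections say withdraw, 5.3.4 is the specific rule, and the replacement sentence in 5.3.3 treats early Grade 3 as a form of leaving the study. This largely stands. A reader might infer that the protocol gives sites flatly contradictory orders, but the natural reading resolves that. What it does not resolve is the unequal AE follow-up.
- **The number affected is visible.** This stands in full. A reader might infer that the count of such patients would be hidden. However, the withdrawal reason goes into the eCRF (5.3.4), and SAP 13.3 plans displays for disposition, end of study and the confirmatory grading check. What no listed display gives is AE observation time beside AE incidence; duration of IMP exposure is a different quantity.
- **What is missed says little about the gel.** AEs are evaluated at Visit 3 itself, ongoing AEs are followed, product-related AEs stay reportable, and worsening sprain symptoms are not AEs. This stands in part. It leaves new events judged unrelated or never brought to the investigator, and these still belong in the planned all-AE rates.
- **Shortened observation also affects other withdrawals, such as loss to follow-up, and the size is assumed.** Both are true. Unlike loss to follow-up, though, this gap is created by a rule and can be avoided with a phone call.

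**Conclusion.** The point holds as a minor design weakness. A stated rule ends active AE collection for dosed patients who remain in the safety denominator, while other early stoppers are followed to Day 14. For withdrawal at the Day 4 check, the downward bias in all-AE incidence is about 0.07 to 0.68 percentage points at assumed Grade 3 rates of 1% to 10%, and less if AEs cluster early. The figures rest on three assumptions: the Grade 3 rate, the timing of AEs, and an AE rate borrowed from an earlier trial.

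A reader might go further and infer a biased safety comparison between arms or a failed detection aim. The documents support neither. Re-grading exists because pain and swelling can mislead the Day 1 grading, and nothing shows it would act differently by arm. The replacement rule preserves planned observation time, so the 1% detection aim is kept. Efficacy is not affected, nor is follow-up of Grade 3 found after Day 4.

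**What to change.** Amend Protocol 5.3.4 and 7.2.4 so that dosed patients withdrawn for Grade 3 sprain have AE follow-up by visit or phone until Day 14, as 5.3.3 already provides, unless consent is withdrawn. One added sentence should say that 5.3.4 governs Grade 3 up to Day 4 and 5.3.3 governs later cases. The cost is about one phone contact per affected patient.

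SAP section 7 lists a hardlock transfer on 29.03.2021. For data already locked, only the reporting step applies: show AE observation time for these patients, by arm, beside AE incidence. Their number per arm can be taken from the planned disposition and grading displays, so this adds one table line.
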